Impact of combining rTMS with motor training (Aim 2b): Motor training strategies used in individuals with cervical SCI often focus on increasing volitional arm muscle activation through strength training, electrical stimulation, and general exercises (see Spooren et al., 2009). While these studies reported that motor training enhances hand motor function, behavioral improvements remain limited. Over the last decades, high frequency rTMS applied over the motor cortex has been shown to induce changes in motor cortical excitability (see section above). Since the mechanisms underlying these effects are related to CNS plasticity, rTMS has been combined with motor training as a tool for enhancing motor function in individuals with movement disorders.

Impairment in motor function is a major deficit in veterans with spinal cord injury (SCI). While rehabilitative interventions have shown success in improving aspects of hand motor function their overall effects remain limited. The goals of this study are to examine the physiology of nervous system pathways contributing to the control of movements after cervical SCI, and to promote the recovery of upper and lower extremity movements by using non-invasive brain stimulation and motor training. We focus on both hand and arm function, which are necessary for most of our daily-life activities, as well as lower extremity movement; therefore, our results may directly impact the quality of life for veterans and their caregivers by enhancing their independence and level of care.

C. Study Design

This study will focus on two basic aspects involved in upper and lower extremity motor function, and how these are affected after chronic SCI using a randomized sham control design with single blind.

Methodology:

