(B). Motoneuronal excitability (reflected by F-wave persistence and amplitude): F-waves will be tested by using supra-maximum stimulus intensity (120% of the maximal motor response) to the ulnar nerve at the wrist and the median nerve at the elbow. The anode and cathode will be approximately 3 cm apart and 1 cm in diameter. We will examine F-waves in first dorsal interosseous, flexor and extensor carpis radialis muscles.

Phase 2

Aim 2a. Enhance recovery of motor function by using non-invasive repetitive transcranial magnetic stimulation (rTMS)

To accomplish this aim we propose to complete two main experiments. First we will use rTMS to test the hypothesis that *rTMS induced cortical plasticity during movement will enhance voluntary output in hand muscles (as measures by electromyography and Jebsen Taylor Test) after spinal cord injury (Aim 2a)*. Second, we will combine precision grip and wrist training with rTMS to test the hypothesis that *precision grip training outcomes will be enhanced by rTMS induced cortical plasticity (aim 2b)*.

Experiment 1 (Aim 2a)

Participants will be randomly assigned to three groups: (1) rTMS, (2) Sham rTMS and (3) sham rTMS over control brain area. Randomization will be performed by lottery (i.e. Drawing from an envelope a piece of paper indicating the intervention). In the first two groups, rTMS stimulation will be targeting finger and wrist muscles during precision grip and write voluntary contractions. In the last group, rTMS will be applied over the dorsolateral prefrontal cortex (DLPFC) or at the leg presentation of the primary motor cortex, or at other related control area as needed. Each subject will be asked to participate in all sessions separated by a washout period of approximately one week. During testing, subjects will be seated in an armchair with both arms flexed at the elbow by 90 degrees. In each group we will use the same apparatus described in Aim1. At the start of the experiment subjects will perform 3 brief MVCs (3-5s) into index finger abduction and wrists flexion and extension, separated by 30 seconds. The maximal forces will be used to set targets for subsequent submaximal contractions.

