Screening Interview: Identifiable information collected during either the screening interview will be destroyed if the potential subject does not qualify. If the subject does qualify and ultimately enrolls into this research, all information collected will become part of their research record. All security precautions that are reflected in this protocol will apply.

Data Collection and Storage: Research records will be retained in accordance with the Veterans Health Administration (VHA) Records Control Schedule. The Federal Privacy Act protects the confidentiality of medical records. Electronically-stored medical information collected from study participants will be kept on a VA server. Electronic data recorded during experimental sessions will be kept on fully-secured computers (password protected) on a VA server. Unique subject identifiers (i.e., a code accessible only to the PI and AI) will be used to label all electronic data files.

F. Sample Size

Up to 500 participants (250 SCI, and 250 control subjects) will be recruited to participate in this study at the VAMHS and at the University of Miami. Based on our previous protocols testing spinal cord injured subjects and healthy control subjects, we have added a 25% attrition rate to the number of subjects we plan to enroll in the study.

All participants will be between 18 and 85 years of age. We plan to recruit both veterans and non-veterans.

G. Data analysis is consistent with the study objective

Aim 1: Repeated-measures ANOVA and Tukey post hoc test will be used to assess the effect of TASK (rest, precision grip/wrist flexion, and precision grip/wrist extension) and GROUP (SCI, controls) on physiological measurements.

Aim 2a: Repeated measures ANOVA and Tukey post hoc test will be used to determine the effect of TIME (0,10, 30, 60 min after a single rTMS session), STIMULATION (rTMS, sham rTMS over control brain area) on physiological and behavioral measurements.

Aim 2b: repeated measures of ANOVA and Tukey post hoc analysis will be used to determine effects of GROUP (training + rTMS, training + sham rTMS), TIME (sessions number 1,5,10 and follow up 1,2, and 3 months) on physiological outcomes and motor performance.

H. Privacy and Confidentiality:

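### The printed Aim 2a ANOVA lists two of the three planned stimulation conditions, so the same-site sham falls outside the only stated analysis

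*Combined protocol and SAP*

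**What the plan says.** Section C, Study Design, describes the trial as "using a randomized sham control design with single blind". Under Phase 2, the Aim 2a hypothesis is that "rTMS induced cortical plasticity during movement will enhance voluntary output in hand muscles"; it names no comparator.

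The Experiment 1 (Aim 2a) text then says:

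- Conditions: "Participants will be randomly assigned to three groups: (1) rTMS, (2) Sham rTMS and (3) sham rTMS over control brain area".
- Site of conditions 1 and 2: "In the first two groups, rTMS stimulation will be targeting finger and wrist muscles during precision grip". Condition 2 is therefore a sham at the same target as the active condition.
- Site of condition 3: "In the last group, rTMS will be applied over the dorsolateral prefrontal cortex (DLPFC) or at the leg presentation", or another control area.
- Allocation: "Randomization will be performed by lottery (i.e. Drawing from an envelope a piece of paper indicating the intervention".
- Attendance: "Each subject will be asked to participate in all sessions separated by a washout period of approximately one week".

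The paragraph on measurements before and after the rTMS protocol lists MEPs, SICI, F-waves, EMG and force on both occasions.

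Section G gives the Aim 2a analysis as a repeated-measures ANOVA with Tukey post hoc tests and the factors "TIME (0,10, 30, 60 min after a single rTMS session), STIMULATION (rTMS, sham rTMS over control brain area". It states no baseline level, covariate, change score or normalisation, and no other section gives an Aim 2a analysis.

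**The concern.** The design and the analysis do not list the same conditions. An analyst who followed section G literally would leave out the sham that shares its target with the active condition. That comparison isolates the effect of stimulation from the effect of where the coil is placed. What remains is rTMS at one site against a control-area condition at another.

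The consequence depends on what condition 3 is. Its label in both Experiment 1 and section G says sham, but the Experiment 1 description says rTMS is applied there. If it is sham, the trial still has a sham comparison but loses the site-matched one. If it is active, the printed model compares two active sites and contains no sham, contrary to the design stated in section C.

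Two further matters are left open. The text assigns subjects to three groups yet has each of them attend every session, and this decides the error term for STIMULATION. The pre-rTMS measurements are collected, but section G gives them no role. If none of this is settled beforehand, the sham, the contrast, the error term and the use of baseline could all be chosen after the data are seen.

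**Working it through.** The plan gives no sample size, power, alpha or effect size specific to Aim 2a, so there is no figure of its own to reproduce. The check is a count of factor levels, followed by the cost and possible gain of the changes.

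**Conditions and contrasts**

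- Experiment 1 has 3 conditions: rTMS, same-site sham and the control-area condition. Pairwise contrasts: 3 × 2 / 2 = 3.
- Section G has 2 STIMULATION levels. Pairwise contrasts: 2 × 1 / 2 = 1.
- The second printed level carries the label of condition 3, so the missing level is condition 2. Both contrasts that involve the same-site sham are absent.
- With the four printed times, STIMULATION has 1 degree of freedom as printed and 2 with all conditions. The interaction has 1 × 3 = 3 and 2 × 3 = 6.

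**Cost of restoring the third condition**

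Alpha is not stated; 5% two-sided is assumed. The large-sample critical value for one pair is 1.96, and for Tukey over three pairs about 2.34. The ratio is 2.34 / 1.96 = 1.19, so a simultaneous interval is about 19% wider for the same standard error. The key contrast does not bear this cost if it is prespecified and tested first, outside the Tukey family.

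**Between- or within-subject factor**

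- For between-subject: the word groups, and a lottery that draws an intervention.
- For within-subject: each subject attends all sessions after a washout. Section G also labels its between-subject factors in Aims 1 and 2b GROUP, but labels this one STIMULATION.
- Calling the model repeated-measures does not decide the matter, because TIME is repeated under either design.

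The balance points to a within-subject factor, but the text does not say so.

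**Pre-rTMS value**

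All four TIME levels (0, 10, 30 and 60 min) are described as after the session, so none is a baseline. The factors below give the variance of a contrast at one post time after covariate adjustment, relative to the post-only contrast. The documents give no correlations, so all of them are assumptions.

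- Crossover, with within-session pre-post correlation rw and between-session correlation rb: 1 − [(rw − rb)/(1 − rb)]².
  - rw = 0.7, rb = 0.5: 1 − (0.2/0.5)² = 0.84
  - rw = 0.7, rb = 0.7: 1 − 0 = 1.00
  - rw = 0.9, rb = 0.5: 1 − (0.4/0.5)² = 0.36
  - rw = 0.9, rb = 0.7: 1 − (0.2/0.3)² = 0.56
- Parallel groups, with pre-post correlation r: 1 − r². For r = 0.7 this is 0.51; for r = 0.9 it is 0.19.

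In a crossover the gain therefore runs from nothing to a reduction of nearly two thirds in variance.

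**The case against.** The strongest reply is that this is a typing slip. Adding the words for the same-site sham to the printed list restores the three conditions of Experiment 1, and nothing says that data from condition 2 would be discarded. This is probably right about the cause, and a reader who inferred a deliberate decision to drop the same-site sham would go beyond the text. The slip still needs correcting, because section G is the only stated Aim 2a analysis and its second level reads as a complete, correctly labelled condition.

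A second reply is that the printed contrast already meets the sham-controlled design if condition 3 is sham, as it is labelled in both places. That stands. A reader might infer that Aim 2a has no sham comparison at all. The documents support this only if condition 3 is active, and the phrase suggesting so is weak evidence, because the same text also speaks of rTMS stimulation for the sham group. Nor do the documents name the same-site sham as the key comparator; that is inferred from section C and the shared target.

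Third, section G does not propose a between-subject error term for data from all sessions, so a wrong standard error cannot be charged to the plan. The gap is that the structure is not stated.

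Fourth, a reader might infer that a post-only analysis is biased. Under random allocation or random session order it is not. Omitting the baseline is a question of precision, and its value depends on correlations nobody has given. It is also separate from the missing sham, which follows from the STIMULATION list alone.

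**Conclusion.** The point holds as a mismatch between design and analysis that should be fixed. Three Aim 2a conditions are planned and two are analysed as printed, which leaves one of three contrasts and no site-matched sham comparison. If condition 3 is sham, the loss is that comparison and the condition 2 data. If it is active, the printed model has no sham. The documents do not settle which applies.

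The conclusion about the missing condition rests on the printed text and on no numerical assumption. Three further statements do rest on assumptions or inference: the choice of key contrast, the Tukey critical values (5% alpha, large sample), and the precision factors for baseline adjustment (assumed correlations). The baseline matter is secondary. Aim 2b is not affected, since section G compares training plus rTMS with training plus sham rTMS there.

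**What to change.** 1. In section G, Aim 2a, list STIMULATION with all three conditions. Name rTMS versus same-site sham as the key contrast, and say whether it is tested first or within the Tukey family.

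2. In Experiment 1, reconcile the label and the description of condition 3 (sham or active), and reconcile assignment to three groups with attendance at all sessions. If STIMULATION is within-subject, as the evidence suggests, use a subject effect and a period term, and have the lottery draw a session order. If it is between-subject, say so and use the matching error term.

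3. Secondarily, for the outcomes measured before and after rTMS (MEPs, SICI, F-waves, EMG and force), adjust for the pre-rTMS value in a form fixed in advance once the design is settled. Two outcomes need care. The Jebsen Taylor test is named in the hypothesis but not in that before-and-after list, so a pre-rTMS value in each session is not explicit. For force, the feedback after rTMS is set from performance before it, so the generic precision factors may not carry over.

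The cost is wording in sections C and G and slightly more analysis. The same-site sham sessions and the listed pre-rTMS measurements are already planned, so these changes need no new visits or participants. The only statistical price is the higher Tukey critical value, where that family is used.

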This study will consist of electromyography (surface and intramuscular), peripheral nerve stimulation, and transcranial magnetic stimulation, electrical stimulation, of the hand, arm, leg, and foot representation of the primary motor cortex, as well as MRI scans of the brain. We will examine the physiological measurements of upper and lower extremity muscles (such as in the first dorsal interosseous (FDI), biceps brachii (BIC), anterior deltoid (AD), tibialis anterior (TA), hamstring (HAMS) and quadriceps (QUAD)). This study may occur at the Miami Project to cure Paralysis at the University of Miami. We will include subjects between the ages of 18 and 85, both healthy controls and individuals with chronic spinal cord injuries that occurred at least 6 months prior to recruitment. Both healthy controls and those with spinal cord injuries will be able to perform small hand and arm movements and small leg and foot movements. The primary outcome measures of this study are muscle responses to stimulation with magnetic pulses using TMS and electrical stimulation of a peripheral nerve in the arm or leg. We propose to enhance the recovery of motor function by using new protocols of high frequency non-invasive repetitive TMS (rTMS) and motor training. Repetitive TMS will be used during hand, arm, leg and foot movements in a task-dependent manner to induce cortical plasticity and enhance voluntary output of the muscles associated with those movements. Second, rTMS will be applied in a task-dependent manner during a visuo-motor training task that also involves movements of the hands, arms, legs or feet.

Phase 1

Aim 1. Neural Control of Movements in SCI and Control Subjects

We will use TMS, CMEPS, and peripheral nerve stimulation to test the hypotheses that 'precision grip and wrist movements will be associated with reduced motor cortical (as measured by intracortical inhibition) and spinal inputs (as measured by F-wave persistence and amplitude) to hand and wrist motoneurons after cervical SCI compared to controls'. Subjects will be instructed to perform a precision grip (between index and thumb) and simultaneously wrist flexion or extension movements. Measurements of cortical and motoneuronal excitability will be acquired during movement.

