Lower Extremity Physiological Examination Components:

Range of Motion (ROM): active ankle and hip ROM will be measured by a motion capture system (Opti Track, V120: Tri camera, NaturalPoint, Inc) in sitting and standing position. In sitting, subjects will be instructed to complete maximal voluntary dorsiflexion for 10 times separated for period of 10 sec of rest. In standing, subjects will be instructed to complete maximal voluntary hip flexion for 10 times separated for period of 10 sec of rest. Trunk movements will be avoided during testing. The motion capture system will also be utilized to measure foot drop and hip flexion. Markers will be positioned on the external line of the mid trunk, hip, knee, external malleolus, and the lateral side of the 5th metatarsophalangeal joint. The elevation of the toe above ground level will be taken as a measure of foot drop. The amplitude of toe elevation will be calculated from the distance between the marker placed on the 5th metatarsophalangeal joint and the ground (Barthélémy et al., 2010). The largest distance between these two points will be determined and will be referred to as the highest toe elevation. The presence or absence of the second toe elevation prior to heel strike will be measured by subtracting the excursion of the malleolus marker from the elevation of the toe. Hip angle will be constructed by using the trunk, hip and knee markers.

Pinch Grip Strength:

Will be assessed bilaterally using load cells that will record the force generated by the subject. Force will be applied by the thumb and index finger and will be recorded in Newtons (N).

Modified Ashworth Scale and Pendulum Test:

Will be used to measure spasticity level in subjects with SCI during soft tissue stretching.
(Modified Ashworth Scale; Bohannon and Smith, 1987)

Phase 3

Experiment 2 (Aim 2b) :

Individuals with SCI and healthy controls will be randomly assigned to two groups: (1) training + rTMS, and (2) training + sham rTMS. Randomization will be the same as described above. Training will be complete in approximately 15 sessions over approximately 3 weeks. In each session, stimulation or sham stimulation (approximately 25 minutes) will be applied during precision grip and wrist visuo-motor training (approximately 1 hour).

Training + rTMS group- Training will consist of executing three different grip forces with one hand and simultaneously wrist flexion and extension movements while the contralateral hand is at rest.

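### Aim 2b's repeated-measures ANOVA leaves out the collected baseline and SCI/healthy status and does not define its session levels; a baseline-adjusted mixed model on all available data is more precise

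*Combined protocol and SAP*

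**What the plan says.** Section G plans, for Aim 2b, that "repeated measures of ANOVA and Tukey post hoc analysis will be used to determine effects of GROUP" (training with active or with sham rTMS) and "TIME (sessions number 1,5,10 and follow up 1,2, and 3 months) on physiological outcomes and motor performance". No baseline covariate is named, and there is no rule for participants who miss a visit.

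Four other places bear on this:

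- **Measurement schedule** (Plan for assessment of long-term effects; Phase 3 follow-up). Measurements are taken on both sides of the first, fifth and tenth sessions and at three monthly follow-ups. That makes 3 × 2 + 3 = 9 occasions for six TIME levels. One of them is a true baseline, taken before any stimulation.
- **Who is randomised** (Phase 3, Experiment 2). "Individuals with SCI and healthy controls will be randomly assigned to two groups". The Aim 2b model has no term for this, whereas the Aim 1 model has TASK "and GROUP (SCI, controls) on physiological measurements".
- **Attrition** (section F). "we have added a 25% attrition rate to the number of subjects we plan to enroll in the study". This is a study-wide figure, with no timing and no Aim 2b rate.
- **Training length** (Phase 3, Experiment 2). Training runs for about 15 sessions, while the measurement plan and the TIME factor stop at session 10.

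**The concern.** Aim 2b is a randomised comparison with a baseline measured on everyone, yet the planned model does not use that baseline as a covariate. It pools two populations that the protocol itself expects to differ. The Phase 1 hypothesis predicts reduced intracortical inhibition and reduced spinal inputs ("as measured by F-wave persistence and amplitude) to hand and wrist motoneurons after cervical SCI compared to controls"), and the same measures are Aim 2b outcomes.

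The session levels are also undefined. If session 1 means the pre-session value, one of the six levels is untreated. If it means the post-session value, baseline is not in the model at all.

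Finally, classical repeated-measures ANOVA needs a value at every level. If it is run that way, a participant who misses one follow-up month also drops out of the session-10 comparison. What is at stake is mainly precision, together with a clear statement of which contrast is tested.

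**Working it through.** **Inputs.** From the documents: two arms, six TIME levels, nine occasions, 25% attrition, up to 500 participants. Assumed: correlation r between baseline and a later value of 0.5 to 0.7; an SCI/healthy gap d of 0.5 to 1.5 within-population SDs in a 50:50 mix; the timing of loss.

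1. **The plan's own figure.** 500 equals 375/(1 − 0.25) or 400 × 1.25. Neither 375 nor 400 is in the documents, and no power, effect size, SD, correlation or Aim 2b sample size is given. The 500 can therefore be neither reproduced nor faulted, and the results below are relative.

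2. **Baseline.** In units of single-visit variance, an unadjusted visit contrast has 1, a change contrast 2(1 − r), and a baseline-adjusted contrast 1 − r².
   - r = 0.5: 1, 1.00 and 0.75.
   - r = 0.7: 1, 0.60 and 0.51.
   - Adjusted over change is (1 + r)/2 = 0.75 or 0.85, a saving of 25% or 15%.
   - Adjusted over unadjusted is 0.75 or 0.51, a saving of 25% or 49%.
   - These depend on r, not on which visit is compared.

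3. **Keeping incomplete participants**, if the ANOVA is complete-case. The session-10 variance ratio (all available over completers, both baseline-adjusted) is roughly the completer fraction over the fraction observed at session 10.
   - All 25% lost after session 10: 0.75/1.00 = 0.75.
   - Loss spread evenly over five post-baseline visits: 0.75/0.90 = 0.83.
   - All lost before session 10: 0.75/0.75 = 1.00; correlated earlier values recover only 0-3% of the standard error.
   - Simulation (five assumed covariance settings, 50 and 100 per arm, 1,000-1,500 runs) gives 0.72-0.79 for late loss and 0.79-0.85 for spread loss, so 15-28% lower.
   - At month 3 under dropout it gives 0.95-1.01, from 5% lower to 1% higher. An exact calculation with a correlation of 0.9 between adjacent visits, decaying with distance, and all loss in follow-up reaches 0.87.
   - With isolated misses instead of dropout (5.6% per visit; 1 − 0.944⁵ = 0.25), the ratio is 0.73-0.82 at session 10 and 0.76-0.80 at month 3.

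4. **Combined**, with session 1 as pre-session baseline, spread loss and the change contrast as comparator. At a constant correlation of 0.5, session 10 gives 0.75 × 0.83 = 0.62, a standard error 21% lower; month 3 is 15% lower. With correlation decaying from 0.7 between adjacent visits, the reductions are 22% and 25%.

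5. **SCI/healthy status.** Leaving it out adds q = d²/4 to the variance of an unadjusted GROUP contrast: 0.06, 0.25 and 0.56 at d = 0.5, 1 and 1.5. With baseline in the model, the residual is (1 + q) − (r + q)²/(1 + q), against 1 − r² with the term.
   - d = 1.5, r = 0.5: 1.5625 − 1.0625²/1.5625 = 0.84, against 0.75 (12% more).
   - d = 0.5, r = 0.7: 0.515, against 0.51 (1% more).
   - A level difference that is stable over time subtracts out of a change or GROUP × TIME contrast.

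6. **Meaning of session 1.** If it is the pre-session value, the GROUP main effect of a constant effect δ is (0 + 5δ)/6 = 5δ/6. The interaction is not diluted.

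7. **Bias.** The simulation used a true effect of 0.50 SD, 60 per arm, and 25% dropout after session 10 driven by the session-10 change. With the same dropout mechanism in both arms, completers give 0.47-0.51 and the mixed model 0.49-0.51.

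**The case against.** The strongest defence is that the plan never says completers only. A reader might infer that session-10 data will be thrown away, but section G names no deletion rule and no software. What can be said is that the plan is silent, and that the loss follows if the classical form is used.

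A reader might also place the benefit mainly at session 10. That is true only of the gain from keeping incomplete participants, and only if much of the loss comes later. The documents give no timing for attrition, and the baseline gain applies at other visits too.

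Nor does the missing status term harm every contrast. The 6-56% inflation and the 5/6 dilution apply to the GROUP main effect (the inflation also to a raw visit contrast), and section G does not say which effect decides.

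Over-enrolment also protects the plan. If the 25% allowance restores an assumed 0.80 power (noncentrality 2.80, two-sided 5%), completers have 2.80 × √(1.25 × 0.75) = 2.71, power 0.77, or 2.80 × √(0.75/0.75) = 2.80, power 0.80. The documents therefore do not show an underpowered comparison. The point is that the same participants could give more: 0.88-0.90 at session 10 if all loss is later.

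The simulations used maximum likelihood with 50 or more per arm. Performance in a smaller Aim 2b sample, with small-sample degrees of freedom, was not tested.

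These objections limit the size and scope of the point. They do not answer the unused baseline, the absent status term or the undefined TIME levels.

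**Conclusion.** The concern holds as a matter of precision and specification. The baseline gain (15-25% or 25-49% of variance, by comparator) is the firmest part, since it needs only an assumed correlation of 0.5-0.7. The missing-data gain is conditional on a complete-case analysis and on when participants leave. The status term matters for unadjusted GROUP contrasts and adds only 1-12% once baseline is in.

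A reader might go further and call the planned analysis biased. The documents do not support that: appreciable bias at session 10 needs dropout that depends on outcome differently in the two arms, and nothing in the plan suggests it.

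Confidence is medium, because no Aim 2b sample size, SD, effect size or correlation is given.

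**What to change.** Replace the Aim 2b ANOVA with a linear mixed model on all available data from randomised participants:

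- **Terms.** GROUP, TIME and GROUP × TIME; the pre-session-1 value as covariate and SCI/healthy status as factor, each with its TIME interaction. Add a GROUP × status term, or report the GROUP contrast within SCI, because the stated objective is recovery after SCI.
- **TIME.** Define one value per level, with only post-baseline levels as outcomes. Pre-session values at sessions 5 and 10 plus the three follow-ups would be one choice. Post-session values also carry the same-day after-effect that Aim 2a follows over "TIME (0,10, 30, 60 min after a single rTMS session".
- **Key contrast.** First reconcile the approximately 15 training sessions with measurement and TIME levels that end at session 10. Then name one GROUP contrast at one level, for one outcome from the class the protocol calls primary ("The primary outcome measures of this study are muscle responses to stimulation with magnetic pulses using TMS and electrical stimulation of a peripheral nerve").
- **Estimation.** Unstructured covariance, a prespecified simpler fallback, and small-sample degrees of freedom such as Kenward-Roger.
- **Missing data.** State the missing-at-random assumption and add one sensitivity analysis, for example delta-adjusted imputation at month 3 with shifts of 0 to 0.5 SD in either arm. With 25% missing, the largest shift moves the contrast by 0.25 × 0.5 = 0.125 SD.

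The cost is SAP wording, some programming and one sensitivity analysis; no new data are needed. The downsides are more covariance parameters (k(k + 1)/2 = 15 for five levels, 21 for six), reliance on missing at random, and little gain at month 3 from keeping incomplete participants under dropout. If dropout in one arm depends on the unseen month-3 change (odds ratio 2 per SD), the mixed model returns 0.61-0.63 or 0.37-0.40 for a true 0.50, no better than completers. That is why the sensitivity analysis is needed.
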